3.1. STUDY MEASURES

[figure not shown]
The outline of the study was presented on session 3.

Initial Visit: Enrolment (Visit 1): Baseline demographic data will be recorded at the time of study enrolment including age, sex, chronic kidney disease (CKD) etiology, Charlson comorbidity index, history of polycystic kidney disease, previous abdominal surgery and presence of hernias, catheter technique placement.

The following anthropometric measurements are required:

- 1) Height: measured standing with shoes off
- 2) Weight: measured with shoes off and “empty” of dialysis fluid. If weighed with fluid in PD the fill volume should be subtracted to give a “dry weight”
- 3) The distance from the decubitus plane to mid-axillary line measured using the method described below:
 - a. The decubitus plane is defined as the bed or couch with the patient lying supine (Figure 2 (A))
 - b. The mid-axillary line is found by:
 - i. The patient raises their arm above the head.
 - ii. Locating the apex of the armpit, the deepest part of the armpit that the hand can reach.
 - iii. The midaxillary line is the line parallel to the ground from the apex of the axilla downward along the lateral chest wall. (Figure 2 (B))
 - iv. A level ruler is used to parallel to the ground to align its midline with the midaxillary line located in the previous step.
 - c. Using another level ruler perpendicular to the ground to measure the distance from the midaxillary line to the decubitus plane

- 4) Waist circumference: measured with a tape measure wrapped above the iliac crests around the level of the umbilicus. See Figure 2 (C).

Created in BioRender.com 

Figure 2 Measurements required to estimate IPP: The patient is placed fully supine on a couch (A). The couch defines the decubitus plane, while the mid-axillary line is identified- the distance between these two planes is measured (B). Waist circumference is measured above the iliac crests at the level of the umbilicus (C).

At Visit 1, 2 and 3 the following information will also be recorded: PD modality, prescribed day and night intra-peritoneal volume, adequacy and peritoneal function using peritoneal equilibration test (PET) data, number of peritonitis episodes, hernias, and leakages developed during PD treatment.

The GSRS will be administered at each Visit 1, 2 and 3 using paper questionnaires. At Visit 1 patients who have started dialysis will be asked to recall symptoms in the month prior to starting dialysis.

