3.2. STUDY OUTCOMES

The primary outcome will be the incidence of non-infectious PD-related complications identified by the clinical team caring for the patient including the development of a new:

- Hernia
- Pleuroperitoneal fistula (PPF)
- Patent processus vaginalis (PPV)
- Retroperitoneal leak

The secondary outcome will be:

- changes in patient reported outcome measures on the GSRS at 3 and 12 months following study recruitment.referral for surgical fixation of non-infectious PD-related complications
- modality change to APD
- transfer to haemodialysis due to the non-infectious complications

During the period of 12 months from study enrolment. Radiological imaging is not required for confirmation nor is surgical fixation.

In Visit 2 and 3, participants who 1) refuse to fill in the GSRS questionnaire, 2) loss of adequate mental capacity to fill in the GSRS questionnaire, 3) refuse to consent clinicians to record their: PD modality, prescribed day and night intra-peritoneal volume, adequacy and peritoneal function using peritoneal equilibration test (PET) data, number of peritonitis episodes, hernias, and leakages developed during PD treatment, 4) defaulted follow-up visits, 5) become pregnant, and 6) received renal transplantation, will be recorded as early withdrawal from the study. Their reason to be withdrawal will be recorded. Data before withdrawal will still be used in outcome analysis. Participants who are withdrawing early from the study will receive same standard and schedule of care.

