6. ASSESSMENT AND FOLLOW-UP

All candidates will be followed up for 12 months following initial eIPP measurement. The formal end of this study will be 12 months after the eIPP measurement of the 150th incident cohort patient. No further recruitment to the prevalent cohort group will take place after the recruitment of the 150th incident patient. Incidental findings will not be recorded and reported in this study. Only the outcome mentioned in Section 3.2 will be recorded and analysed. Participants will be advised to report incidental findings to their GP and clinical care team as per local guidelines or standard of care.

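### Declining the GSRS at Visit 2 or 3 counts as early withdrawal, and no available text provides for collecting the primary outcome afterwards

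*Combined protocol and SAP*

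**What the plan says.** Section 3.2 (Study Outcomes) gives six reasons, applying at Visits 2 and 3, for which a participant "will be recorded as early withdrawal from the study". The first covers "In Visit 2 and 3, participants who 1) refuse to fill in the GSRS questionnaire". The third is a different refusal: "3) refuse to consent clinicians to record their: PD modality" and the other clinical items, which include hernias and leakages. Declining the form and declining clinical data recording are therefore distinct, and either one is enough.

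The section then says two things about withdrawn participants. On data: "Data before withdrawal will still be used in outcome analysis". On care: "Participants who are withdrawing early from the study will receive same standard and schedule of care". It does not mention outcome data arising after withdrawal.

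In the same section, the primary outcome is a set of complications "identified by the clinical team caring for the patient", with neither imaging nor surgery needed for confirmation. Change in GSRS is listed as a secondary outcome.

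Three other places bear on the point:

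- Section 3.1 (Study Measures): "At Visit 1, 2 and 3 the following information will also be recorded", a list that includes hernias and leakages.
- Section 6: "All candidates will be followed up for 12 months following initial eIPP measurement".
- Section 7.1: the sample size allows for no drop-out.

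**The concern.** A participant who will not complete a symptom form, but is content for complications to be recorded, is treated as having left the study. The natural reading of a withdrawal rule that keeps only earlier data is that later complications are not collected. These are data the study could still have, because the patient stays under the same clinicians on the same schedule and those clinicians identify the events.

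Two things are at stake. One is loss of primary-outcome information in a study whose sample size has no allowance for it. The other is bias. Section 1.1 itself suggests that high intraperitoneal pressure may go with bloating and early satiety. If symptoms affect willingness to complete a gastrointestinal questionnaire, refusal may depend on eIPP, and the loss would then differ between the groups being compared. Section 7 plans descriptive statistics only, so nothing says whether withdrawn participants stay in the incidence denominator.

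**Working it through.** **The text, side by side**

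| Question | Where | Answer |
|---|---|---|
| Is declining the GSRS alone a withdrawal? | 3.2, item 1 | Yes |
| Is it separate from refusing clinical data recording? | 3.2, item 3 | Yes |
| Does the primary outcome need the GSRS? | 3.2 | No; the treating team identifies it |
| Which data are kept? | 3.2 | Those from before withdrawal |
| Is later outcome collection provided for? | 3.2 | Not mentioned |
| Does the 12-month follow-up statement address withdrawn participants? | 6 | No |
| Does any clause keep participants in follow-up? | 8.2 | Yes, but only where the clinician gives a different treatment |

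Section 3.1 also contains a sentence on GSRS refusal that breaks off. It is not relied on.

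**Follow-up lost per participant**

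Visit 2 falls on day 60 to 120 and Visit 3 on day 320 to 380 (section 3.1). The outcome window is 12 months, taken as 365 days.

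- Visit 2: 365 − 120 = 245 days to 365 − 60 = 305 days, or 67% to 84% of the window.
- Visit 3: at most 365 − 320 = 45 days, and none if the visit falls after day 365.

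**The plan's own sample size**

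Section 7.1 gives 146 for 36% vs 17%, alpha 0.05 and power 0.8. With equal groups and a two-sided pooled two-proportion formula I get 84 per group, 168 in total, so 146 does not reproduce. That is a separate matter. It is noted here only because it explains the baseline power below.

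**Illustration of size**

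Assumptions not in the documents: equal groups of 73, a two-sided test, a constant hazard over the year, and the withdrawal rates.

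- P(d) = 1 − (1 − p)^(d/365). At day 90, P = 0.1042 for p = 0.36 and 0.0449 for p = 0.17.
- Counted event-free: observed rate = p(1 − w) + w·P(d), where w is the share withdrawn.
- Excluded if event-free at withdrawal: that rate divided by 1 − w(1 − P(d)), with n reduced by the same factor.
- Power = Φ{[|p1 − p2| − 1.96·√(p̄(1 − p̄)(1/n1 + 1/n2))] / √(p1(1 − p1)/n1 + p2(1 − p2)/n2)}.

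With no withdrawal, expected events are 73 × (0.36 + 0.17) = 38.7. Power is Φ[(0.19 − 1.96 × 0.0731)/0.0713] = 74.4%. At 75 per group, the recruitment minimum of 150, it is 75.6%.

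Withdrawal at day 90, equal in both groups:

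| Withdrawn | Rates if counted event-free | Events lost | Power, counted event-free | Power, excluded |
|---|---|---|---|---|
| 2% | 35.5% vs 16.7% | 0.6 (1.4%) | 73.6% | 73.8% |
| 5% | 34.7% vs 16.4% | 1.4 (3.6%) | 72.4% | 72.8% |
| 10% | 33.4% vs 15.7% | 2.8 (7.2%) | 70.3% | 71.1% |
| 20% | 30.9% vs 14.5% | 5.6 (14.4%) | 66.0% | 67.3% |

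Moving the withdrawal from day 60 to day 120 changes the events lost from 8.1% to 6.3% (10% withdrawn) or from 16.2% to 12.6% (20% withdrawn). Counted event-free, power runs from 70% to 71% and from 65% to 67%. At day 320 the losses are only 1.0% and 2.1% of events, with power 74% and 73%.

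**If withdrawal differs by eIPP** (day 90, true difference 19 points):

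| Withdrawn, high / low eIPP | Counted event-free | Excluded |
|---|---|---|
| 30% / 10% | 28.3% vs 15.7%: 12.6 points, power 45% | 38.7% vs 17.4%: 21.3 points, power 74% |
| 10% / 30% | 33.4% vs 13.2%: 20.2 points, power 83% | 36.73% vs 18.57%: 18.2 points, power 59% |

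The sign of the distortion depends both on who withdraws and on a denominator rule the plan does not state.

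**The case against.** The strongest reply is that section 3.2 does not say outcome collection stops. The withdrawal label could be administrative, and section 6 promises 12 months of follow-up for everyone without exception. That is right as far as the literal wording goes, and the days lost are a consequence of the natural reading, not of an express instruction. But section 6 does not mention withdrawn participants, and the specific rule in 3.2 limits itself to earlier data. Sites following it would have reason to stop. At the least, the two sections must be reconciled.

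The text available is also incomplete: the flow diagram is not shown and a sentence in 3.1 on this topic is cut off. The finding is therefore limited to the text that can be read.

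On size, no refusal rate is given. Entry requires willingness to comply with study procedures, so low rates are plausible, and at 2% to 5% the power loss is about one to two percentage points. The 30%/10% splits have no basis in the documents and show possibility only. If events cluster before Visit 2, less is lost. The low baseline power and the missing denominator rule are faults elsewhere in the plan, not products of this rule. All of that stands.

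The retention clause in section 8.2 shows that the protocol has such wording available, but it concerns a change of treatment and says little about intent here. Finally, continued record review depends on consent wording that was not available for review, for form refusal as well as for loss of capacity.

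**Conclusion.** The concern holds. Declining a secondary-outcome form is made a withdrawal from the study, separately from refusing clinical data recording, and no available text provides for collecting the primary outcome afterwards. It should be fixed.

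The loss falls almost entirely on refusals at Visit 2. Uniform loss is modest: on the stated assumptions, 10% to 20% withdrawn around day 90 costs about 4 to 8 percentage points of power. The more serious risk is loss related to eIPP, which could shrink or enlarge the contrast. Its likely size cannot be judged from the documents. The textual defect depends on none of these illustrations. Confidence is medium, because the text does not expressly end collection and the refusal rate is unknown.

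Loss of capacity (item 2) and defaulted visits (item 4) are less clear. The first depends on consent. For the second, the number of missed visits is not stated, while hernias and leakages are recorded at visits. Pregnancy and transplantation (items 5 and 6) are outside this point.

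**What to change.** Amend section 3.2 as follows:

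- **GSRS not completed (item 1):** record the GSRS as missing at that visit. The participant stays in the study, and the primary and clinical secondary outcomes are taken from the treating team's records to 12 months.
- **Loss of capacity (item 2):** continue record review where the consent given permits it.
- **Defaulted visits (item 4):** state how many missed visits count as defaulting, and specify retrieval of outcomes from records for missed visits.
- **End of collection:** among items 1 to 4, only refusal of data recording (item 3) or explicit withdrawal of consent ends it.

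Bring section 6 into line, and state in section 7 how participants whose collection does end enter the incidence denominator.

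The cost is amendment wording, a check that the consent covers continued record review (especially after loss of capacity), and some record review for participants who miss visits. No extra visits are needed.

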The estimated IPP will be assessed at Visit 1 using the equations included in Appendix 2 with the Li formula used for the primary outcome measure.

For the prevalent and incident cohorts. Visit 1 will take place at the time of study enrolment. Visit 2 will take place alongside a routine clinic visits between 60 to 120 days after enrolment (2-4 months). Visit 3 will similarly take place between 320 and 380 days (11-13 months) after study enrolment.

Participants who refuse to fill in the GSRS questionnaire or

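### A defaulted visit is recorded as study withdrawal and no complication status is required at exit, so primary-outcome events known to the treating team need not be captured

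*Combined protocol and SAP*

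**What the plan says.** Section 3.2 defines the primary outcome as the incidence of new hernia, pleuroperitoneal fistula, patent processus vaginalis or retroperitoneal leak within 12 months of enrolment. The treating team identifies these events, and neither imaging nor surgery is needed to confirm them.

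Section 3.1 sets the recording points: "At Visit 1, 2 and 3 the following information will also be recorded". The list that follows includes "number of peritonitis episodes, hernias, and leakages developed during PD treatment". Visit 2 falls 60 to 120 days after enrolment. For the last visit, "Visit 3 will similarly take place between 320 and 380 days (11-13 months) after study enrolment".

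Section 3.2 lists six grounds for early withdrawal at Visits 2 and 3. The last three read: "4) defaulted follow-up visits, 5) become pregnant, and 6) received renal transplantation, will be recorded as early withdrawal from the study". The reason is to be recorded, and "Data before withdrawal will still be used in outcome analysis".

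Section 6 says: "All candidates will be followed up for 12 months following initial eIPP measurement".

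Section 5 asks for all adverse events to be reported, and for serious ones to reach the Chief Investigator within 24 hours. Section 7.1 assumes 0% dropout. The data analysis section specifies descriptive statistics and gives no rule for denominators, censoring or missing data.

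**The concern.** Two features of Section 3.2 act together.

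First, a defaulted visit is itself a ground for withdrawal. That would be reasonable if the outcome had to be measured at the visit. It does not: a hernia or leak diagnosed in routine care is in the patient's notes whether or not the study visit took place. Only the GSRS needs the participant's attendance.

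Second, nothing about the outcome is requested at withdrawal. Take a patient who completes Visit 2 at day 90, develops a hernia at day 150 and is transplanted at day 300. The hernia arose on PD, under consent, within the outcome period. Section 3.2 asks the site for a withdrawal and a reason. No instruction asks for the hernia or its date.

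At stake are the completeness of the primary outcome and the precision of the eIPP comparison, in a plan that allows nothing for dropout.

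**Working it through.** **Recording points.** Visit 1 is enrolment, so new events have two scheduled recording points. The gap between them is at least 320 − 120 = 200 days and at most 380 − 60 = 320 days. Entries are cumulative, so a later visit would pick up an earlier event, but a withdrawn participant has no later visit.

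**The plan's own figures.** The plan gives no withdrawal rate and no estimate of missed events. The event rates used below, 36% with high IPP and 17% with low IPP, come from Section 7.1. The sample size given there, 146, is not reproduced by a two-sided 1:1 comparison of these rates, which gives 168 (84 per group). That is a separate matter and nothing below depends on it.

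**Assumptions.** There are 150 patients in a cohort. Withdrawal is uniform over 365 days and independent of events, and no event is captured outside visits. The average 12-month risk is (36% + 17%)/2 = 26.5%, so the expected number of events is 150 × 0.265 = 39.8.

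**Step 1: unrecorded time before withdrawal.** With Visit 2 at day V, the mean time from last completed visit to withdrawal is [V²/2 + (365 − V)²/2]/365.

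- V = 60: (1,800 + 46,512.5)/365 = 132 days
- V = 90: (4,050 + 37,812.5)/365 = 115 days
- V = 120: (7,200 + 30,012.5)/365 = 102 days

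Mean time to withdrawal is 182.5 days, so the unrecorded share is 73%, 63% and 56%.

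**Step 2: events not captured before withdrawal.** With risk spread evenly, this is n × 0.265 × gap/365.

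- 15 withdrawals (10%): 3.975 × 102/365 = 1.1, up to 3.975 × 132/365 = 1.4
- 30 withdrawals (20%): 7.95 × 102/365 = 2.2, up to 7.95 × 132/365 = 2.9

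**Step 3: check with a constant hazard.** Take 75 patients per group, Visit 2 at day 90 and Visit 3 at day 365, with yearly hazard λ = −ln(1 − p). For a withdrawn patient:

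- The chance of an event by withdrawal is 1 − p/λ: 0.193 (high) and 0.088 (low).
- The chance of an event recorded at Visit 2 is (275/365) × (1 − e^(−90λ/365)): 0.079 and 0.034.

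Withdrawn patients stay in the denominator, and power is two-sided. With no withdrawal it is 75.6%. Missed events are taken from unrounded values.

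| Withdrawn | Events captured, visits only | Events captured, status check at exit | Missed | Power, visits only | Power, with check |
|---|---|---|---|---|---|
| 10% | 36.6 | 37.9 | 1.3 | 71% | 73% |
| 20% | 33.5 | 36.0 | 2.5 | 66% | 70% |
| 30% | 30.4 | 34.1 | 3.8 | 61% | 67.5% |

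The 10% and 20% rows agree with Step 2.

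**Step 4: defaulted Visit 2.** If 15 patients default Visit 2 and are withdrawn, their expected events over the year are 15 × 0.265 = 4.0. With the default at day 60 to 120, about 0.7 to 1.3 of these fall before it (3.975 × 60/365 and 3.975 × 120/365), and about 3.3 to 2.7 fall after it. If these are the same patients as in Step 2, the two totals must not be added.

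**Step 5: effect on the comparison.** In Step 3 at 20% withdrawal, the captured risks are 30.4% and 14.3%. The risk ratio is 2.13, against 0.36/0.17 = 2.12 with full capture. The risk difference falls from 19.0 to 16.1 percentage points.

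**The case against.** The strongest reply is that silence is not exclusion. Section 3.1 names three recording points without ruling out others, and a hernia before a transplant is, on plain reading, data before withdrawal. Because the outcome is identified in routine care, the event is in the notes. A new hernia or leak also meets the adverse event definition, and an unplanned admission for one would need a serious adverse event form. A reader might infer that these events are lost, that withdrawal leaves no record, or that withdrawn patients are counted as event-free. None of this is supported: the route of capture is unspecified, the withdrawal and its reason are recorded, and no denominator rule is given.

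What remains is that no text requires the notes to be read at withdrawal, and none says that adverse event reports feed the primary outcome. Practice could differ between sites.

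It can also be said that Section 6 states a general rule and Section 3.2 its exceptions, which is a normal arrangement. That is fair for transplant. It is weaker for a defaulted visit, which does not stop the outcome from being known. Section 3.2 also does not say how many defaulted visits are needed.

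A reader might further infer that the eIPP association is biased towards no effect. That does not follow: if the same proportion of events is missed at high and low eIPP, the risk ratio is unchanged in expectation.

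Lastly, two figures are absent from the text available to me, and a sentence near the end of Section 3.1 about participants who refuse the GSRS breaks off. An exit step there cannot be excluded, but the withdrawal paragraph in Section 3.2 describes none.

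**Conclusion.** The point holds as a gap in what the plan requires. Recording a defaulted visit as withdrawal ends collection of a primary outcome that needs no visit, and nothing asks for complication status or dates up to the time of any withdrawal.

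The size is modest and rests on assumed withdrawal rates: about 1–3 of about 40 events at 10–20% withdrawal, costing about 2 to 4 points of power. Defaults add the events that follow them, with up to about 4 of 40 missed over the year if 15 patients default Visit 2. Any capture through adverse event reports or the notes would reduce these figures. If complications themselves cause missed visits, the loss would be larger.

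The consequences are lower precision, and understated incidence if withdrawn patients stay in the denominator. Bias in the relative association with eIPP would require the loss to differ by eIPP, and the documents give no evidence on that.

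**What to change.** Amend the withdrawal paragraph in Section 3.2 as follows:

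1. Record a defaulted visit as a missed visit, not a withdrawal. Take complications for that interval from the clinical record and still attempt Visit 3.
2. For participants who are withdrawn, except those who refuse data recording, record the withdrawal date, and complication status with event dates from the clinical record up to that date.

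Confirm that the consent wording covers reading the clinical record without a study visit.

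The cost is one paragraph of text and a few minutes of note review per affected patient. Clinical care does not change.

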4. PARTICIPANT ENTRY

4.1. PRE-REGISTRATION EVALUATIONS

No pre-registration evaluations are required. All patients with kidney failure treated with peritoneal dialysis are eligible.

4.2. INCLUSION CRITERIA

- Age 18 years or older
- Diagnosis of end-stage renal failure requiring peritoneal dialysis as renal replacement therapy
- Ability to give informed consent and comply with study procedures.

4.3. EXCLUSION CRITERIA

- Known allergy or hypersensitivity to any component of the dialysis solution.
- Inability or unwillingness to comply with study procedures.

